8.6.4 Criteria and procedures for subject's withdrawal or discontinuation

Any subject may voluntarily discontinue the study at any time without prejudice. The Investigator may discontinue a subject from the study at any time if (s)he considers that remaining in the study compromises the subject's health or the subject is not sufficiently cooperative. In either event, reason(s) for discontinuation should be recorded on a study withdrawal form, provided as part of the CRFs for the study. Possible reasons for study discontinuation include the following:

- AE necessitating discontinuation from the study
- The subject is lost to follow-up
- Voluntary decision to withdraw consent made by the subject⁶
- Investigator decision⁷
- Other reason

In case of a subject lost-to-follow-up, the Investigator must attempt to contact the subject (or relative/family contact) by phone, email or letter at least three times. If attempts are unsuccessful, the 'subject withdrawal' form is to be completed in the study file and reported, as appropriate, in required reports to the Sponsor, EC and TGA.

During surgery, an alternative device (e.g., CI522 or CI512) may be implanted in subjects where there are substantial difficulties with the CI532. These subjects will continue the clinical investigation and their outcomes will be compared to those subjects who received the CI532 device.

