8.7.2.1 Determination of hearing preservation post CI532 implantation

Unaided air conduction (AC) hearing thresholds will be reported for all participants at six months and twelve months post-activation to support the primary efficacy endpoint.

The population implanted with the CI532 device (per protocol population) will be divided into two groups for analysis:

1. Participants with a total hearing loss (no measureable AC threshold at audiometer limits at each frequency)
2. Participants with preserved hearing (measureable AC threshold at 250, 500 and 750 Hz)

Hearing preservation post CI532 implantation will be considered to be functional hearing preservation as defined by the Cochlear consensus¹²:

- i. Unaided AC hearing thresholds ≤ 70 dB HL at 250 Hz
- ii. Unaided AC hearing thresholds ≤ 90 dB HL at 500 Hz
- iii. Unaided AC hearing thresholds ≤ 90 dB HL at 750 Hz

The number of participants with a total hearing loss, preserved hearing and preserved functional hearing post CI532 implantation will be reported for each frequency (250, 500 & 750 Hz¹³).

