9 STATISTICAL CONSIDERATIONS

All subjects who are recruited to the clinical investigation will constitute the intention-to-treat (ITT) population for the purposes of safety evaluation. Only subjects implanted with the CI532 will be considered as the completed cases (CC) population and per protocol (PP) analysis of the primary endpoint will be performed.

Where the CC population is insufficient, the sponsor reserves the right to ask the centres to recruit additional cases in order to reach the desired sample size of 12. As this is a feasibility clinical investigation, there have been no formal power or sample size estimations performed for the primary objectives.

To understand if measurable low frequency thresholds can be maintained with implantation using the CI532 cochlear implant and fit with the acoustic component:

1. Audiometric data will be summarized at each follow-up time point to assess any changes in hearing sensitivity and to characterize the impact of the procedure on residual hearing.
2. The degree of hearing will be reported and tabulated as the number of subjects who have measurable residual hearing post CI532 implantation.

The number, severity and relationship of adverse events will be reported and tabulated. The rate of device-related adverse events will be compared to known rates of device-related adverse events for the commercially approved Nucleus cochlear implants.

Pre- to post-operative gains in speech and SSQ scores will be tested using paired comparisons (Student's t or non-parametric test if more appropriate). GBI scores will be compared to a hypothesised mean score of 0 (no benefit).

There are no pass/fail criteria to be applied to the results of the clinical investigation.

If required an interim analysis and report on three month speech and hearing threshold data will be provided for the purposes of submission to the TGA.

The characteristics of the study group will be presented descriptively. Quantitative variables such as age will be presented with mean, standard deviation, median, minimum and maximum and 95% CI. Qualitative variables such as age or gender will be presented as percentages and observed frequencies. If differences in outcome are found for subgroups defined by baseline age or gender, analyses will be performed to explore the possible role of other baseline characteristics to explain the results.

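### Preserved and functional hearing are counted only in CI532-implanted subjects, with no companion count over all attempted CI532 insertions; whether 12 means enrolled or CI532-implanted also needs stating

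*Combined protocol and SAP*

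**What the plan says.** **Populations.** Section 9 uses all recruited subjects for safety: "All subjects who are recruited to the clinical investigation will constitute the intention-to-treat (ITT) population for the purposes of safety evaluation". For the primary endpoint it narrows the population: "Only subjects implanted with the CI532 will be considered as the completed cases (CC) population and per protocol (PP) analysis of the primary endpoint". Section 8.7.2.1 does the same for hearing preservation: "The population implanted with the CI532 device (per protocol population) will be divided into two groups for analysis". The counts of total loss, preserved hearing and functional hearing that follow are all framed as outcomes after CI532 implantation.

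**Conversions.** Section 8.6.4 provides that "During surgery, an alternative device (e.g., CI522 or CI512) may be implanted in subjects where there are substantial difficulties with the CI532". Section 8.7.7 likewise names the back-up device for a tip fold-over that persists after re-insertion. On what happens to these subjects in the study, Section 8.6.4 continues: "These subjects will continue the clinical investigation and their outcomes will be compared to those subjects who received the CI532 device". Section 8.7.2.1 adds: "Unaided air conduction (AC) hearing thresholds will be reported for all participants at six months and twelve months post-activation".

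**Other hearing summaries.** Section 7 plans a number and percentage with complete loss of hearing. The supportive analyses at the end of Section 9 plan proportions improved, unchanged and worse on audiometry. Neither names its population.

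**The target of 12.** Section 8.6.5 gives 12 as the total enrolled and provides for replacement of pre-operative withdrawals. Section 9 says that, if the CI532-implanted population falls short, "the sponsor reserves the right to ask the centres to recruit additional cases in order to reach the desired sample size of 12". Under Section 8.6.6 enrolment comes before surgery.

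**The concern.** Whether a subject is in the hearing-preservation count depends on an intra-operative outcome of the device and technique under test. A converted subject has normally had at least one attempted CI532 insertion, and Section 4.2 lists complete loss of residual hearing as a possible result of inserting the electrode. Section 3 says the study population was chosen to show that the electrode design and insertion technique are atraumatic. Section 9 says audiometric data will be summarised "to characterize the impact of the procedure on residual hearing". For either purpose, attempted insertions are a relevant denominator. The protocol's own glossary (Section 22.2) warns that per-protocol analysis is open to bias because it leaves out enrolled subjects, yet no companion count is planned.

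What is at stake is how a descriptive figure is read. Section 3 says the results may support a randomised multi-centre study of functional hearing preservation, so a proportion from this study may be carried forward. The uncertain meaning of 12 adds to this. After one conversion the study could end with 12 enrolled and 11 CI532-implanted, or 13 enrolled and 12 CI532-implanted. Because the top-up is optional, the denominator could be settled after conversions are known.

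**Working it through.** **The plan's own figure.** The sample size of 12 has no derivation to reproduce. Sections 8.6.3 and 9 state that no power or sample-size estimation was done.

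**Input: conversion rate p.** The documents give no rate for the current assembly. Section 3 reports 34 successful CI532 implantations in the ongoing multicentre study and one tip fold-over that ended in exchange for a CI512. I assume that this exchange counts as an intra-operative conversion (the timing is not stated) and that it is additional to the 34, so p = 1/35 = 2.9%. Risk is taken as constant and independent across cases.

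**Chance that the two denominators differ.**
- P(no conversion) = (34/35)^12 = 0.706.
- P(at least one) = 1 − 0.706 = 0.294.
- If the exchange was one of the 34, p = 1/34 and P(at least one) = 0.301.
- The temporal-bone fold-over rate of 3/110 (Section 3), used only as a proxy, gives 0.282.
- The exact 95% interval for 1/35 is 0.07% to 14.9%. Putting those limits into 1 − (1 − p)^12 gives 0.009 to 0.856, so the rate is poorly known.

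**Effect of one conversion.** The numbers preserved among CI532 recipients (6 or 9) are illustrative.

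| Scenario | CI532-implanted | All attempted, converted subject lost hearing | All attempted, converted subject kept hearing |
|---|---|---|---|
| Top-up to 12 implanted | 6/12 = 50.0% | 6/13 = 46.2% (−3.8) | 7/13 = 53.8% (+3.8) |
| Top-up to 12 implanted | 9/12 = 75.0% | 9/13 = 69.2% (−5.8) | 10/13 = 76.9% (+1.9) |
| No top-up, 12 attempted | 6/11 = 54.5% | 6/12 = 50.0% (−4.5) | 7/12 = 58.3% (+3.8) |
| No top-up, 12 attempted | 9/11 = 81.8% | 9/12 = 75.0% (−6.8) | 10/12 = 83.3% (+1.5) |

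**Average effect with top-up, every converted subject losing hearing.** Let K be the number of conversions before 12 CI532 implantations, which is negative binomial: P(K = k) = C(11 + k, k) p^k (1 − p)^12. At p = 1/35, E[K] = 12p/(1 − p) = 12/34 = 0.353. The expected difference E[x/12 − x/(12 + K)] is 1.3 points for x = 6 and 2.0 points for x = 9.

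**Against sampling error.** The exact 95% interval for 6/12 is 21% to 79%, far wider than any shift above.

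**The case against.** The strongest reply is that the CI532-implanted count answers the question the protocol asks. The first primary objective (Section 5.1.1) concerns outcomes after CI532 implantation. The Section 9 phrase about the impact of the procedure sits under a lead-in about implantation using the CI532, and is met there by summarising audiometric data rather than by a count. That stands: the planned count is not wrong and should stay.

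A reader might infer that converted subjects disappear. They do not: Sections 8.6.4 and 8.7.2.1 keep them in follow-up, compare them and report their thresholds. A reader might also infer that no hearing count could include them. That goes too far, because the complete-loss percentage in Section 7 and the change proportions in Section 9 name no population and might cover everyone. They do not close the gap, since neither is a count of preserved or functional hearing.

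Nor do the documents establish that the planned count is biased upward. That requires converted subjects to lose hearing, and the table shows the shift reversing if they keep it. An all-attempts count also includes hearing in ears carrying a CI522 or CI512, so converted subjects must be shown separately.

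A larger effect could be drawn from the 23% back-up rate in the early feasibility trial (Section 3), which would give a 96% chance of at least one conversion in 12. That rate belongs to the version 1 assembly, since redesigned, and is a poor guide to this study.

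Finally, the two statements about 12 can be read together as a planned enrolment with a discretionary top-up. They are loosely worded rather than plainly contradictory.

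**Conclusion.** The point holds as a minor one. The preserved and functional hearing counts use a denominator that depends on how the CI532 insertion went, and no count over all attempted insertions is specified beside them. On the assumed rate of about 1/35 there is a 71% chance that the two counts coincide and a 29% chance that they differ. A single conversion moves the proportion down by about 4 to 7 points if that subject lost hearing, or up by about 2 to 4 points if not. The average overstatement of 1.3 to 2.0 points applies only with top-up and if every converted subject loses hearing. The rate itself rests on one event of unstated timing.

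There is no hypothesis (Section 5.2) and no pass/fail criterion (Section 9), so no error rate or decision is affected; only the reading of a descriptive figure is. The meaning of 12 is a matter of wording to reconcile.

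**What to change.** Keep the CI532-implanted counts and make these additions to Sections 7, 8.6.5, 8.7.2.1 and 9:

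1. Beside those counts, give the same preserved and functional hearing counts at six and twelve months over all subjects with an attempted CI532 insertion.
2. Show converted subjects on a separate line, with observed thresholds and the device received. As a sensitivity analysis, count them as not preserved with the CI532.
3. Name the all-attempted population for the Section 7 complete-loss percentage and the Section 9 change proportions.
4. Report how many insertions were attempted, how many were converted, and how many subjects were added after surgery.
5. Reconcile Sections 8.6.5 and 9 on whether 12 means enrolled or CI532-implanted.

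No new data are needed, because converted subjects already continue with the scheduled audiograms. The cost is one extra table row with its separate line, a protocol amendment, and a figure that may be slightly less favourable.

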8.6.3 Number of subjects required

The protocol describes a feasibility study within a single site and a limited number of subjects (12 subjects) to characterise the audiological outcomes and the feasibility of fitting of the acoustic component postoperatively associated with the CI532 cochlear implant in adult cochlear implant candidates. As such, there have been no power or sample size estimations performed. It is estimated to take six months to recruit this number of subjects. The enrolment period will be extended if required.

⁵ As judged by the investigator i.e. able to complete the speech perception assessment tasks and questionnaires.

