9.1 Missing Data

All efforts will be put forth to ensure near complete follow-up, with particular focus on the assessment of the primary outcomes and occurrence of adverse events. A reminder of subject follow-up due date will be provided to participating centres to facilitate scheduling of the follow-up visit.

In the event a subject is withdrawn prior to the six month post-activation assessment (audiometry), the analysis of the primary endpoint will involve imputing the data point captured (candidacy, activation or three months post activation) for the six month post-activation assessment. The p-value for the primary statistical endpoints will be calculated using this imputation to understand the impact of missing data on the primary results.

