22.2 Other definitions

Term	Description
CA	Competent Authority
CER	Clinical Evaluation Report
EC	Ethics Committee
IB	Investigator's brochure is a compilation of the current clinical and non-clinical information on the investigational device(s) relevant to the clinical investigation.
ITT analysis	The comparison of the treatment groups for all subjects as originally allocated after randomisation to avoid bias.
PASS	Post-authorization safety studies mandated by medical device regulators
PIC	Patient Informed Consent form
PIL	Principal Investigator List
PMS	Post-market surveillance studies
PP analysis	The comparison of treatment groups that includes only those subjects who completed the treatment originally allocated according to the protocol (i.e. a complete dataset). This form of analysis is open to bias as it does not include comparison of treatment groups for all subjects enrolled into the investigation.

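### The per-protocol set carries conflicting labels, and Section 9.1 leaves open whether the primary six-month hearing result is imputed or observed

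*Combined protocol and SAP*

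**What the plan says.** All references are to the combined protocol and SAP.

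**Who is in the primary set**

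- Section 9: "Only subjects implanted with the CI532 will be considered as the completed cases (CC) population and per protocol (PP) analysis of the primary endpoint". Membership depends on the device received, yet the set is named after completion.
- Section 8.7.2.1: "The population implanted with the CI532 device (per protocol population) will be divided into two groups for analysis". Again, membership follows from implantation.
- Section 22.2 (glossary): a PP analysis "includes only those subjects who completed the treatment originally allocated according to the protocol (i.e. a complete dataset"). Here membership follows from having full data.

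**What happens to a subject withdrawn before the six-month audiometry**

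- Section 9.1 first says that "the analysis of the primary endpoint will involve imputing the data point captured (candidacy, activation or three months post activation").
- The next sentence says that a p-value will be calculated "using this imputation to understand the impact of missing data on the primary results".

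**Size and purpose**

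- Section 9 lets the sponsor ask for more cases if the completed-cases population falls short, "in order to reach the desired sample size of 12". Section 8.6.3 confirms that "there have been no power or sample size estimations performed".
- Section 5.2 states no formal hypothesis, and Section 9 sets no pass/fail criteria.

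**The concern.** Take a subject who receives a CI532 and withdraws at month four. Sections 8.7.2.1 and 9 keep this subject in the per-protocol set by device received. The completed-cases label and the glossary would leave the subject out. The first sentence of Section 9.1 puts the subject into the primary analysis with a substituted value. The second implies primary results that exist without that substitution. Nothing in the document ranks these statements.

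The descriptive figures are this study's result. Section 6 asks for the percentage of subjects fitted with the acoustic component, Section 7 for the percentage with complete hearing loss, and the end of Section 9 for proportions improved, unchanged or worse on the audiometry endpoint. Each needs a denominator. Section 3 adds that the findings may support a later randomised study. With 12 subjects, one subject is 1/12 = 8.3 percentage points. The study is unblinded (Section 8.1), so the choice between readings could be made with the data in view.

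**Working it through.** The plan has no figure to reproduce: 12 is a target without a calculation. The check sets the readings side by side and counts under each.

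**Inputs from the plan**

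- Target of 12 subjects (Sections 8.6.3 and 9).
- Entry thresholds of 40 to 65 dB HL at 250 and 500 Hz (Section 8.6.1).
- Functional cut-offs of at most 70 dB HL at 250 Hz and at most 90 dB HL at 500 and 750 Hz (Section 8.7.2.1).
- Values that may stand in for month six: candidacy, activation or three months (Section 9.1).

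**Assumptions, since the plan gives none**

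- w = number of implanted subjects withdrawn before six months, 0 to 3.
- x = number of completers with preserved hearing.
- k = number of the w imputed values that count as preserved, 0 to w.

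**Formulas**

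- Completers only (glossary reading): x / (12 − w).
- All implanted, with Section 9.1 imputation: (x + k) / 12.

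**Main example: w = 2, x = 8**

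- Completers: 8/10 = 80.0% (exact 95% interval 44.4 to 97.5).
- Imputed, k = 0: 8/12 = 66.7% (34.9 to 90.1).
- Imputed, k = 1: 9/12 = 75.0% (42.8 to 94.5).
- Imputed, k = 2: 10/12 = 83.3% (51.6 to 97.9).

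**Other cases**

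| w | x | Completers only | Imputed, k = 0 to k = w |
|---|---|---|---|
| 0 | 9 | 9/12 = 75.0% | 9/12 = 75.0% |
| 1 | 8 | 8/11 = 72.7% | 8/12 to 9/12 = 66.7% to 75.0% |
| 2 | 5 | 5/10 = 50.0% | 5/12 to 7/12 = 41.7% to 58.3% |
| 3 | 7 | 7/9 = 77.8% | 7/12 to 10/12 = 58.3% to 83.3% |

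**Direction.** (x + k)/12 exceeds x/(12 − w) exactly when k/w exceeds x/(12 − w). Imputation therefore raises the figure when the imputed values are preserved more often than the completers are, and lowers it when less often. In the main example, k = 2 gives 1.0 against 0.8 (higher), and k = 1 gives 0.5 against 0.8 (lower).

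**What a candidacy value does.** At entry the threshold is at most 65 dB HL at both frequencies. Since 65 ≤ 70 and 65 ≤ 90, a candidacy value carried forward counts as functional preservation at 250 and 500 Hz whatever the surgery did. Entry sets no limit at 750 Hz, so the result there is not automatic. Section 9.1 does not say which value to use when a subject has more than one.

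**Two related loose ends**

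- Section 8.6.5 replaces only pre-operative withdrawals, while the Section 9 top-up depends on the completed-cases population. Whether a withdrawal after implantation can trigger a top-up depends on the same label.
- Section 9.1 speaks of a p-value and its imputation rule concerns audiometry, but Section 9 names tests only for speech, SSQ and GBI scores. The p-value does not show which audiometric analysis is primary.

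**The case against.** The best defence is that the operative text is consistent. Sections 8.7.2.1 and 9 use the same criterion, and imputing for a withdrawn subject makes sense only if that subject is in the set. The glossary entry speaks of comparing treatment groups, and the neighbouring ITT entry speaks of randomisation; neither fits a single-arm study. A specific definition given twice should prevail over a generic one. There is also no hypothesis, error rate or decision rule to damage. Section 9.1 commits to near-complete follow-up, and one or two withdrawals among 12 can be shown plainly in any report.

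Most of this stands. It disposes of three stronger inferences that a reader might draw:

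- *That membership of the primary set is wholly undetermined.* The operative sections favour inclusion. The glossary and the label create a conflict to remove, not an even contest.
- *That a completers-only analysis inflates the result, 80% against 67%.* The plan has no rule counting withdrawals as not preserved. Under Section 9.1, 67% arises only if both imputed values show loss, and 83% is equally possible.
- *That subjects who withdraw will be those who did badly.* Section 8.6.4 lists adverse events among possible reasons for discontinuation, but the documents give no dropout rate or pattern.

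The defence does not answer Section 9.1. Even with the glossary set aside, its two sentences give imputation two different roles, and the plan does not say which result is the primary one.

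**Conclusion.** The point holds as a problem of definition with a limited, conditional effect. A withdrawn CI532 subject most likely belongs in the primary set; whether that subject enters with a substituted value or as missing is not settled. With no withdrawal before six months, every reading agrees. With two withdrawals and 8 of 10 completers preserved, both assumed, the same data support 80% for completers and 67% to 83% with imputation. The direction is not fixed, and the exact intervals overlap widely. Power and error rates are not affected; the reported denominators and proportions are. The most concrete weakness is that a pre-operative threshold may stand in for a six-month one and then counts as functional preservation at 250 and 500 Hz by construction.

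**What to change.** **Section 9.** Define one primary set: all subjects who leave theatre with a CI532, whether or not their data are complete. Remove the completed-cases label, and state the top-up rule in terms of this set.

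**Section 22.2.** Align the PP entry with that definition.

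**Section 9.1.** State that the primary tabulation uses observed six-month audiometry, with withdrawn subjects kept in the denominator under their own category of no six-month data. In the main example this would read 8 preserved, 2 not preserved and 2 without data, out of 12. Make the imputed result a sensitivity analysis that names which earlier value is used and does not carry candidacy thresholds forward as preserved hearing. Make the completers-only result a second sensitivity analysis.

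**Cost.** Wording and a little more tabulation; no new visits, measurements or subjects. The reported percentage may be less favourable: in the example, 8/12 = 67% shown as preserved with 2/12 = 17% unknown, instead of 80% or 83%.

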3 JUSTIFICATION FOR THE DESIGN OF THE CLINICAL INVESTIGATION

A multi-centre clinical early feasibility trial was performed with 17 cases being implanted with version 1 of the electrode array/sheath assembly (3). Electrode tip fold-over was identified in 32% of cases and due to this complication, 23% of cases received a commercial back-up device (CI24RE(CA) or CI512). Complications were related to device deficiencies and surgical protocol deviations. Hearing preservation was generally poor and most subjects lost their residual hearing in the implanted ear. The participants recruited for the early feasibility trial met current local indications for a conventional implant. The inclusion criteria specified an unaided hearing threshold in the ear to be implanted of equal to or better than 80 dB HL at 500Hz. Speech perception in quiet and noise significantly improved pre-operatively-to-post-operatively. Follow-up of these cases is now more than 5 years with no device related adverse events reported – all devices remain functional and in place.

Rotation of the electrode in the sheath may have contributed to the adverse device effects seen in the early feasibility trial and lead to further sheath design by Cochlear Limited. Most of the development focussed on the sheath until version 4 where the sheath to guide-tube assembly was reconfigured to further improve handling and visibility. In the intermediate designs tip folding occurrence was reduced by removing rotation and finally by modification of the slit in the sheath. The slit allows the sheath to be removed after the electrode is fully deployed. The final version improved the stability of the sheath especially when some bending of the array and sheath occurs.

Pre-clinical testing with the CI532 was performed with four versions of the electrode-sheath assembly over four rounds of formal temporal bone trials. The temporal data on the EA32 (using the latest sheath design) shows good perimodiolar position in a large majority of cases with a relatively low potential for intra-cochlear trauma shown by a scala dislocation rate of 3.3%. Once use errors were taken into account the tip fold-over rate was 3/110 or <3%.

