5 OBJECTIVES AND HYPOTHESES

5.1 Objectives

5.1.1 Primary objectives

The primary objectives for the clinical investigation are:

1. To characterise audiometric outcomes post CI532 cochlear implantation in individuals who meet current indications for cochlear implantation but also have pre-operative hearing thresholds between 40 to 65 dB HL at 250 and 500 Hz of in the ear to be implanted.
2. An assessment of medical/surgical and device related adverse events compared to the current approved labelling with regard to type, frequency and seriousness at six months post-activation to evaluate safety.

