8.2 Endpoints

8.2.1 Primary endpoints

The six month post-activation visit serves as the primary endpoint for data collection related to efficacy and safety outcomes post-CI532 implantation:

1. Efficacy endpoints

- 1.1. Hearing in the implanted ear will be reported as the change in pure-tone air-conduction thresholds (dB HL) pre-operatively to post-activation according to the Cochlear consensus at six months post-activation and 12 months post-activation.

Audiometric data will be summarized at each follow-up time point to assess any changes in hearing sensitivity and to characterize the impact of the procedure on hearing.

To understand if measurable low frequency thresholds can be maintained with implantation using the CI532 cochlear implant and fit with the acoustic component

- 1.2. Assessment of speech recognition in quiet will be measured using the CNC monosyllabic word test (7). Assessment of speech recognition in noise will be measured using sentences drawn from the Australian Sentence In Noise (AuSTIN) test (8) with speech-weighted noise (SWN) at a fixed +5 dB SNR.

2. Safety endpoints

- 2.1. Adverse events will be summarized by event type, severity, seriousness, as well as relatedness to the device and implant procedure will be reported and tabulated.

- 2.2. Report of medical/surgical and device related adverse events compared to the current approved labelling with regard to type, frequency and seriousness.

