8.6.5 Subject replacement

The total number of subjects enrolled in the clinical investigation is 12. If a subject withdraws pre-operatively, they will be replaced by a newly recruited subject who meets the selection criteria for participation.

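### The primary safety comparison sets an event rate from about 12 subjects beside unstated known rates with no interval, so it cannot separate a rate equal to the reference from a large excess

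*Combined protocol and SAP*

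**What the plan says.** Primary objective 2 (section 5.1.1) is to assess medical, surgical and device-related adverse events "compared to the current approved labelling with regard to type, frequency and seriousness at six months post-activation to evaluate safety". Section 8.2.1 repeats this as safety endpoint 2.2: "Report of medical/surgical and device related adverse events compared to the current approved labelling with regard to type, frequency and seriousness". Section 9 turns it into a comparison of rates: "The rate of device-related adverse events will be compared to known rates of device-related adverse events for the commercially approved Nucleus cochlear implants".

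Section 9 gives no value or source for the known rates, and no interval, margin or rule for reading the comparison. Its only mention of a 95% CI is in the description of the study group's quantitative variables. Other outcomes are specified more closely: a paired test for speech and SSQ gains, and a null value of 0 for the GBI.

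The safety population is all recruited subjects. Section 8.6.5 states: "The total number of subjects enrolled in the clinical investigation is 12". Section 9 allows further recruitment to reach 12 subjects implanted with the CI532, so the safety denominator is 12 or slightly more.

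The plan is open about its limits. Section 5.2 states no formal hypothesis. Section 9 says that "there have been no formal power or sample size estimations performed for the primary objectives" and "There are no pass/fail criteria to be applied to the results of the clinical investigation".

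The benchmark is named differently in different places: approved labelling in sections 5.1.1 and 8.2.1, commercially approved Nucleus implants in section 9, and the Contour Advance electrode (CI512) in section 7 for complete loss of hearing.

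**The concern.** Frequency of adverse events is part of a primary objective, and the analysis section promises to compare rates. With about 12 subjects and events that may be uncommon, the observed count will often be 0 or 1. A count that small says little about the underlying rate, and without an interval the report would not show how little. An analyst could follow section 9 to the letter by printing 0% or 8.3% next to a reference figure.

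Either result could mislead. Zero events invites the reading that the device is no worse than its predecessors. One event may look like a several-fold excess although the true rate equals the reference. Section 3 says that the outcomes may support the design of a randomised multi-centre trial, so it matters that the safety figures carry their uncertainty with them.

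**Working it through.** **Inputs.** n = 12 (section 8.6.5). The reference rate is not given. The nearest figure in the documents is tip fold-over in temporal bones, 3/110 = 2.7%, after use errors were taken into account (section 3). It concerns this device's own array and is not a comparator adverse-event rate, so it serves only as an illustration. The unit of the rate is not stated either; I take it as the proportion of subjects with at least one event. The plan's figure of 12 comes without a calculation, so there is nothing to reproduce.

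**Step 1: what the data can exclude.** Clopper-Pearson upper limits need no reference rate.

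- 0/12, one-sided 95%: 1 − 0.05^(1/12) = 22.1%. Two-sided 95%: 1 − 0.025^(1/12) = 26.5%.
- 1/12: solve (1−p)^12 + 12p(1−p)^11 = 0.05, giving 33.9%. With 0.025 on the right, 38.5%.
- 2/12: 43.8% one-sided, 48.4% two-sided.

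Even the cleanest result, 0/12, leaves room for a true rate of 22.1%, which is about eight times the illustrative reference (22.1/2.7 = 8.2). A slightly larger safety population changes little: 0/14 gives 1 − 0.05^(1/14) = 19.3%.

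**Step 2: a bare comparison at the illustrative reference.** Let p0 = 3/110 = 0.0273 and 3p0 = 0.0818.

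- No events under a true tripling: (1 − 0.0818)^12 = 0.36.
- At least one event when the true rate equals the reference: 1 − (1 − 0.0273)^12 = 1 − 0.718 = 0.28. One event in 12 is 8.3%, which looks like a threefold excess (8.3/2.7 = 3.1).
- Either 0 or 1 event, from (1−p)^12 + 12p(1−p)^11: 0.96 at the reference and 0.74 at three times the reference. The results that are nearly certain with no excess are also the usual results with a tripling.

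**Step 3: dependence on the missing reference rate.** The p0 values below, other than 2.7%, are assumptions. With X the number of subjects with an event, an excess is seen when X > 12p0.

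| Reference p0 | Tripling not seen: P(X ≤ 12p0), true rate 3p0 | Excess seen though none exists: P(X > 12p0), true rate p0 |
|---|---|---|
| 1% | 0.69 | 0.11 |
| 2% | 0.48 | 0.22 |
| 2.7% | 0.36 | 0.28 |
| 5% | 0.14 | 0.46 |
| 10% | 0.09 | 0.34 |
| 20% | 0.003 | 0.44 |

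A tripling goes unseen more often than not only when (1 − 3p0)^12 > 0.5, that is, when p0 is below about 1.9%. At higher references it is usually seen, but an apparent excess is then also common when there is none. Without an interval, neither kind of result can be interpreted.

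**The case against.** The strongest reply is that this is an openly descriptive feasibility study. It states no hypothesis, no power calculation and no pass/fail criteria, and it tabulates events by type, severity, seriousness and relatedness, so the rate is not the whole safety evaluation. That stands as a defence of the sample size and of the absence of a formal test. It does not explain why a rate comparison named under a primary objective should be shown without its uncertainty.

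Several stronger readings are tempting, and the documents do not support them:

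- A reader might infer that a threefold excess would usually be missed. That holds for a significance test at low reference rates: at 2.7%, an exact one-sided 5% test needs two events and misses a tripling 74% of the time. The plan contains no such test. On the plain comparison it describes, the figure at 2.7% is 36%. If the known rate is about 15% or more, a tripling is not usually missed on either reading.
- A reader might infer that no visible excess will be reported as comparable safety. No section says so. The plan leaves that reading open but does not adopt it.
- A reader might infer that a TGA submission will rest on this comparison. The optional interim report in section 9 covers three-month speech and hearing threshold data, and section 2 says that the device was approved in April 2017.
- A reader might want to test fold-over against the first-version experience, where "Electrode tip fold-over was identified in 32% of cases". Section 3 gives 17 cases, and no count out of 17 yields that percentage (5/17 = 29.4%, 6/17 = 35.3%). It is not a safe benchmark: whether 1/12, with a bound of 33.9%, excludes the earlier rate depends on which count is meant.

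**Conclusion.** The concern holds in a limited form. A primary safety comparison rests on about 12 subjects, an unstated reference rate and no interval. As written, it cannot separate a rate equal to the reference from a large excess: 0/12 is compatible with a true rate up to 22.1% and 1/12 with one up to 33.9% (one-sided 95%). These bounds depend only on n = 12 and on counting subjects with at least one event.

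The probability of overlooking a given excess cannot be fixed from the documents, because they do not state the known rate. The 36% and 28% at 2.7% illustrate the two directions of error and are not estimates for this trial. The gap is one of reporting method. It does not undermine the feasibility aim, and it is cheap to close.

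**What to change.** After the sentence on known rates in section 9, add wording to this effect:

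- The proportion of subjects with a device-related adverse event and, separately, the proportion with tip fold-over will each be reported with an exact (Clopper-Pearson) 95% interval.
- The device-related event proportion will be shown beside one named reference rate with its source. In choosing it, reconcile the approved labelling of section 8.2.1 with the commercially approved Nucleus implants of section 9. If no sourced reference exists for fold-over, give its interval alone.
- The report will state the event rate above which the data exclude.
- Absence of an observed excess will not be described as evidence of comparable safety.

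Do not add a pass/fail criterion or a rule that calls the device no worse when the upper bound does not exceed the reference. The smallest one-sided bound available at n = 12 is 22.1%, so such a rule could never be met for a lower reference, and it would conflict with the plan's own statement that no such criteria apply. Do not add a benchmark against the 32% figure.

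The cost is a few lines of text and of exact binomial output, with no extra subjects. The downside is a less favourable safety statement: with 0 or 1 event, the two-sided interval will exclude only rates above about 26% or 38%.
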